2 LIST OF ABBREVIATIONS

Term	Definition / description
AE	Adverse event
AESI	Adverse event of special interest
ATC classification	Anatomical, Therapeutic, Chemical classification
BI	Boehringer Ingelheim
BM	Bone marrow
BMI	Body Mass Index
BSA	Body Surface Area
BRPM	Blinded report planning meeting
CR	Complete Remission
CRi	Complete Remission with incomplete marrow recovery
CT	Concomitant therapy
CTCAE	Common Terminology Criteria for Adverse Events
CTP	Clinical Trial Protocol
CTR	Clinical Trial Report
DBL	Data base lock
DILI	Drug Induced Liver Injury
DLT	Dose Limiting Toxicity
DMS	Data Management and Statistics
ECG	Electrocardiogram
ECOG	Eastern Cooperative Oncology Group
eCRF	Electronic case report form
EoT	End-of-Text
ICH	International Conference on Harmonisation
iPV	Important protocol violation
IRR	Infusion related reaction
LLQ	Lower limit of quantification
LVSI	Laboratory values of special interest
MedDRA	Medical Dictionary for Regulatory Activities
MQRM	Medical and Quality Review Meeting

MTD	Maximum Tolerated Dose
NE	Not evaluable
PB	Peripheral blood
PD	Progressive disease
PFS	Progression free survival
PK	Pharmacokinetics
PKS	Pharmacokinetic set
PR	Partial remission
PT	Preferred term
PV	Protocol violation
REP	Residual effect period
RP2D	Recommended phase II dose
SAE	Serious adverse event
SD	Standard deviation
SDL	Subject data listings
SOC	System organ class
SOP	Standard Operating Procedure
SS	Screened set
SSC	Special search category
TCM	Trial Clinical Monitor
TF	Treatment failure
TOC	Table of contents
TS	Treated set
TSAP	Trial statistical analysis plan
TTF	Time to treatment failure

3 INTRODUCTION

As per ICH E9, the purpose of this document is to provide a more technical and detailed elaboration of the principal features of the analysis described in the protocol, and to include detailed procedures for executing the statistical analysis of the primary and secondary variables and other data.

This TSAP assumes familiarity with the Clinical Trial Protocol (CTP), including Protocol Amendments. In particular, the TSAP is based on the planned analysis specification as written in CTP section 7 "Statistical Methods and Determination of Sample Size". Therefore, TSAP readers may consult the CTP for more background information on the study, e.g., on study objectives, study design and population, treatments, definition of measurements and variables, planning of sample size, randomisation. This TSAP follows the Boehringer Ingelheim (BI) internal reference ([1](#)).

This TSAP is based on the Project SAP wherever possible. Wordings like "randomisation (first administration of study treatment in non-randomised trials)" should therefore be interpreted as applicable.

SAS Version 9.2 or later version will be used for all analyses.

Version 1 of this TSAP(c01837068-02) fully specified the planned analyses for the population of patients with refractory or relapsed AML. Further enrolment of this population was stopped as of 10-JUN-2016 (for more details refer to CTP amendment 3 and the authorisation letter to continue study cohort 3 in AML patients in complete remission with high risk to relapse). In January 2018, the trial was terminated because of low patient recruitment into the CR population. This version now includes the specifications as to how the data from the CR population will be summarized a final CTR that will includes the analyses for both populations.

4 CHANGES IN THE PLANNED ANALYSIS OF THE STUDY

Clarification of Residual Effect Period (REP):

According to CTP section 6.2.5, for refractory or relapsed AML patients the reporting period for adverse events is defined until 6 weeks (42 days) after last administration of study drug.

However, the residual effect period (REP) for BI 836858 is defined as 30 days. Therefore, for all safety analyses defined in this TSAP, all events occurring between first drug administration until 30 days after last drug administration will be considered on treatment. A separate table or listing will be provided with adverse events outside the on-treatment period. See TSAP [section 7.8](#) for details.

For AML patients in CR a REP of 30 days was defined in the CTP.

For the CR patients, an abbreviated set of tables and listings will be included consisting of:

- Patient disposition
- Patient demographics
- Baseline disease characteristics
- Exposure
- Medication compliance
- Summary table of Adverse Events
- Frequency table of adverse events by highest CTCAE grade
- Frequency table of user defined adverse events by highest CTCAE grade
- Overall summary of infusion related reactions
- Listing of patients with dose related toxicities
- A frequency table of AEs by treatment, system organ class, and preferred term
- Hepatic injury (DILI)
- Listing of hepatic enzymes and bilirubin
- Summary of haemalytic laboratory values

Listings of all clinical efficacy, safety, laboratory and biomarker data will be provided.

5 ENDPOINTS

5.1 PRIMARY ENDPOINTS

The primary endpoints are the maximum tolerated dose (MTD) and the number of patients with dose limiting toxicity (DLT) during the MTD evaluation period.

Maximum tolerated dose (MTD):

MTD is defined as the highest dose studied for which the incidence of dose-limiting toxicity is no more than 17% (i.e., 1/6 patients) during the MTD evaluation period. The MTD will be defined on the basis of DLTs occurring during the MTD evaluation period of dose escalation cohorts. However, all information, including adverse events qualifying for a DLT from later times, will be considered in the final determination of the recommended Phase II dose (RP2D).

MTD evaluation period:

FOR PATIENTS WITH REFRACTORY OR RELAPSED AML,

the MTD evaluation period is defined as the time from the first administration of BI 836858 to start of the fifth administration, excluding the day of fifth administration. In case the fifth infusion will not be started, the evaluation period ends 30 days after the last administration.

FOR AML PATIENTS IN CR WITH HIGH RISK TO RELAPSE,

the MTD evaluation period is defined as the time from the first administration of BI 836858 to start of the third administration, excluding the day of third administration. In case the third infusion will not be started, the evaluation period ends 30 days after the last administration.

In case a patient has not completed the required number of administrations due to BI 836858 related toxicity, he/she will not be replaced and this will be considered as DLT. However, patients who have not completed the required number of administrations of BI 836858 for reasons other than BI 836858 related toxicity will be replaced.

That is, a patient will be considered evaluable for MTD assessment if he/she received at least 4 (refractory or relapsed patients) or 2 (patients in CR) administrations of BI 836858 or if he/she received less than 4 (refractory or relapsed patients) or 2 (patients in CR) administrations due to DLT.

The MTD estimate after the dose escalation part of the trial will be obtained on the basis of DLTs observed during the MTD evaluation period. However, for those patients who receive more than 4 (refractory or relapsed patients) or 2 (patients in CR) administrations of BI 836858, all AEs that constitute a DLT will be considered in the final determination of the dose recommended for Phase II.

The list of patients evaluable for MTD will be confirmed by the Trial Clinical Monitor (TCM) no later than at the last blinded report planning meeting (BRPM) before database lock (DBL) for the clinical trial report (CTR).

5.2 SECONDARY ENDPOINTS

5.2.1 Key secondary endpoints

Not applicable.

5.2.2 Secondary endpoints

FOR PATIENTS WITH REFRACTORY OR RELAPSED AML:

Best overall response

The different categories possible for overall response (at a specific timepoint) are Complete remission (CR), Complete remission with incomplete blood count recovery (CRi), Partial remission (PR), Treatment failure (TF) (i.e. Resistant disease, Aplasia, Indeterminate cause, or morphologic relapse), Progressive disease (PD), and Not evaluable (NE).

Best overall response is defined as the best overall response (CR, CRi, PR, TF, PD or NE in this order) recorded since randomisation (first administration of trial medication in non-randomised trials) until the earliest of progressive disease (PD), death or last adequate disease assessment before new anti-cancer therapy.

In order to evaluate the best overall response, the investigator's assessment as given in the eCRF will be taken into account (no central review and no check versus bone marrow measurement is planned).

Progression free survival (PFS)

For patients with 'event' as outcome for PFS:

- PFS [days] = date of outcome - date of randomisation (date of first administration of trial medication in non-randomised trials) +1.

For patients with 'censoring' as outcome for PFS:

- PFS (censored) [days] = date of outcome - date of randomisation (date of first administration of trial medication in non-randomised trials) +1.

The censoring rules and dates of event or censoring for PFS under different scenarios are specified in [Table 5.2.2:1](#).

Table 5.2.2: 1: Derivation rules for PFS

Situation	Outcome (event or censored)	Date of outcome
Progressed according to disease assessment	event	Date of disease assessment of progression
Death without progression	event	Date of death

Table 5.2.2: 1: Derivation rules for PFS (cont.)

Situation	Outcome (event or censored)	Date of outcome
Alive and not progressed	censored	Date of last disease assessment
No disease assessment performed post-baseline, vital status is unknown or patient is known to be alive	censored	Date of randomisation (or first treatment administration, in non-randomised trials)
Subsequent anti-cancer therapy before progression or death (check interval between start of new medication and earliest of subsequent PD or death)		
Interval <= 7 days	event	Earliest date of disease assessment of progression or death
Interval > 7 days	censored	Date of last disease assessment before initiation of subsequent anti-cancer therapy

Time to treatment failure (TTF)

As some patients will receive the next line of therapy, although no formal PD may be diagnosed at the time when the next treatment is indicated, the Time to treatment failure (TTF) will be derived similarly to PFS, but will consider PD, death or start of next anti-AML therapy as events.

For patients with 'event' as outcome for TTF:

- TTF [days] = date of outcome - date of randomisation (date of first administration of trial medication in non-randomised trials) +1.

For patients with 'censoring' as outcome for TTF:

- TTF (censored) [days] = date of outcome - date of randomisation (date of first administration of trial medication in non-randomised trials) +1.

The censoring rules and dates of event or censoring for TTF under different scenarios are specified in [Table 5.2.2:2](#).

Table 5.2.2: 2: Derivation rules for TTF

Situation	Outcome (event or censored)	Date of outcome
Progressed according to disease assessment, no subsequent anti-cancer therapy	event	Date of disease assessment of progression
Death without progression, no subsequent anti-cancer therapy	event	Date of death
Subsequent anti-cancer therapy before progression or death	event	Date of first administration of subsequent anti-cancer therapy
Alive and not progressed, no subsequent anti-cancer therapy	censored	Date of last disease assessment
No disease assessment performed post-baseline, vital status is unknown or patient is known to be alive, no subsequent anti-cancer therapy	censored	Date of randomisation (or first treatment administration, in non-randomised trials)

FOR AML PATIENTS IN CR WITH HIGH RISK TO RELAPSE:Progression free survival (PFS)

Defined as for refractory/relapsed AML patients, see above.

Time to treatment failure (TTF)

Defined as for refractory/relapsed AML patients, see above.

6 GENERAL ANALYSIS DEFINITIONS

6.1 TREATMENTS

In this Phase I trial, treatments are not randomised (open-label, dose escalation). Different dose levels of the investigational medicinal product can arise. The data will be presented for all dose cohorts separately, in particular patients will be analysed by the treatment group initially assigned in the first treatment course.

“Analysing treatment” will be used for reporting of treatment emergent adverse events (AE) and to differentiate between screening, on-treatment, post-treatment and post-study safety data. The inequalities start date \leq onset date of AE $<$ stop date will determine whether the AE will be assigned to the “analysing treatment” or not. [Table 6.1: 1](#) defines the “analysing treatment period(s)” which will be used for reporting of treatment emergent AEs and safety laboratory parameters.

Table 6.1:1: Definition of analysing treatment periods

Analysing treatment period	Start date (including)	Stop date (excluding)
Screening	Date of informed consent	Date of first administration of trial medication
On-treatment	Date of first administration of trial medication	Start date of ‘Follow-up’
Follow-up	Date of end of REP +1	Start date of ‘Post-study’
Post-study	Last date patient status obtained / last date patient known to be alive + 1 (if patient is lost to follow-up) / date of refusal + 1 day / the date patient died + 1	During the trial: open / empty; after database lock (DBL): DBL + 1 day
MTD evaluation period	Date of first administration of trial medication	For patients with refractory/relapsed AML: Date of fifth infusion or (if the fifth infusion was not administered) Date of last administration of trial medication + 30 days + 1 day For AML patients in CR: Date of third infusion or (if the third infusion was not administered) Date of last administration of trial medication + 30 days + 1 day

Data recorded between the first administration of trial medication until up to 30 days (Residual effect period; REP) after the last administration of trial medication will be considered as on-treatment.

In addition, to justify the MTD determination, AEs occurring during the MTD evaluation period will be presented separately from those occurring during the complete on-treatment period.

The actual treatment codes are defined in the document entitled “5-05-o-c-treatment-setup”, which can be found in the trial's DMS Section 5 within BIRDS. Labels of each analysing treatment period and analysis numbers are provided in the TSAP technical documents “ADS Plan” and “Data guide”.

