6.7 BASELINE, TIME WINDOWS, AND CALCULATED VISITS

Study days and visits will be labelled according to the CTP's flow chart.

Unless otherwise specified, baseline is defined as the time-point closest to but prior to first administration of trial medication in course 1. Note that for some trial procedures (for example body weight, vital signs, laboratory tests) this may be the value measured on the same day trial medication was started. In these cases it will be assumed that the measurements were taken according to protocol, i.e. prior to first intake of any trial medication.

Laboratory values: Baseline is defined as the latest time-point before the very first administration of any trial medication in course 1. For laboratories where not only the examination date but also time are recorded, examination time has to be taken into account when defining baseline. That is, a laboratory value on the same date as the first trial drug administration is considered as baseline value if and only if the time of laboratory value is before or the same as the time of first trial drug administration.

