7.8 SAFETY ANALYSIS

7.8.1 Adverse events

The analyses of adverse events (AEs) will be descriptive in nature. All analyses of AEs will be based on the number of patients with AEs and NOT the number of AEs.

The analyses will be based on BI standards. Adverse events will be coded with the most recent version of MedDRA. The severity of AEs will be scaled according to CTCAE version 4.03.

Reporting will be done according to version 5 of the AE guideline ([6](#)).

For analysis of AE attributes such as duration, severity, etc. multiple AE occurrence data on the CRF, will be collapsed into AE episodes provided that all of the following applies:

- The same MedDRA lowest level term was reported for the occurrences.
- The occurrences were time-overlapping or time-adjacent (time-adjacency of 2 occurrences is given if the second occurrence started on the same day or on the day after the end of the first occurrence).
- Treatment did not change between the onset of the occurrences OR treatment changed between the onset of the occurrences, but no deterioration was observed for the later occurrence.

For each patient, all episodes with the same preferred term (PT) (system organ class, SOC) will be condensed to one AE record using a worst case approach for all AE attributes including CTCAE grading.

The analysis of adverse events will be based on the concept of treatment emergent adverse events, where a treatment emergent AE has an onset in the analyzing treatment period. All adverse events occurring before first intake of trial medication will be assigned to 'screening' and all adverse events occurring after last intake of trial medication + 30 days will be assigned to 'follow-up' (in randomised trials for listings only). For details on the treatment definition, see [section 6.1](#). In addition, a listing will be provided, detailing the actual treatment on the day when the adverse event started.

Adverse events of special interest (AESIs):

Adverse events of special interest (AESIs) are defined in CTP section 5.2.2.1 as infusion related reactions (IRRs) of CTCAE grade ≥ 3 , DLTs (occurring during the MTD evaluation period or repeated treatment courses) and hepatic injury (DILI).

Other significant AEs:

Other significant AEs are defined as serious and non-serious AEs that lead to dose reduction or permanent discontinuation of study medication. Their incidence will be reported by severity according to CTCAE grades.

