7.8.2 Laboratory data

The analyses of laboratory data will be descriptive in nature and will be based on BI standards (7). The same on-treatment period as considered for the analysis of AEs will be applied for laboratory values. Patients having at least one post-baseline laboratory value will be displayed in the descriptive analyses.

Descriptive statistics, including change from baseline and frequency of patients with transitions relative to the reference range, will be provided. CTCAE grades for applicable laboratory parameters will be calculated according to CTCAE version 4.03. The following outputs will be presented:

- Worst CTCAE grade experienced during the on-treatment phase.
- Transitions of CTCAE grade from baseline to worst laboratory value, from worst to last laboratory value during the on-treatment phase, and from baseline to last laboratory value.

Patients with missing CTCAE grade at baseline or no baseline value but post baseline values will be displayed in the category “Missing CTCAE grade at baseline”.

Possible clinically significant abnormal laboratory values:

Possible clinically significant abnormal laboratory values are defined as those laboratory values that are of CTCAE Grade ≥ 2 and show an increase from baseline value by at least one CTCAE grade. For those parameters for which no CTCAE has been defined, BI standard definition will be used to determine possible clinical significance. Frequency of patients with possible clinically significant abnormal laboratory values will be provided whenever applicable. If no baseline value is available but the patient has a post-baseline laboratory value of CTCAE Grade ≥ 2 an increase from baseline will be assumed, i.e. the laboratory value considered as possible clinically significant.

Hepatic injury:

As defined in the CTP a hepatic injury (DILI) is defined by the following alterations of hepatic laboratory parameters:

- an elevation of AST and/or ALT >3 fold ULN combined with an elevation of total bilirubin >2 fold ULN measured in the same blood draw sample, and/or
- marked peak aminotransferase (ALT, and/or AST) elevations ≥ 10 fold ULN

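### The SAP sets the on-treatment start by calendar date but the laboratory baseline by clock time, so its table and text disagree on whether a Day 1 pre-dose sample is also an on-treatment value

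*SAP*

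**What the plan says.** Five statements in the SAP bear on this point. Day 1 here means the calendar day of the first administration.

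- **Section 6.1, Table 6.1:1.** The on-treatment row gives "Date of first administration of trial medication" in the column for included start dates. The Screening row gives the same date in the column for excluded stop dates. The table contains no clock time.
- **Section 6.1, scope.** The periods are those "which will be used for reporting of treatment emergent AEs and safety laboratory parameters". The date inequality that goes with them "will determine whether the AE will be assigned to the" analysing treatment; it is worded for adverse event onset.
- **Section 6.1, text under the table.** "Data recorded between the first administration of trial medication until up to 30 days" after the last administration counts as on-treatment.
- **Section 6.7.** For some procedures, laboratory tests among them, baseline can be a Day 1 measurement: "this may be the value measured on the same day trial medication was started". Where laboratory times are recorded, a Day 1 value is baseline "if and only if the time of laboratory value is before or the same as the time of first trial drug administration".
- **Section 7.8.2.** "The same on-treatment period as considered for the analysis of AEs will be applied for laboratory values".

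For adverse events, section 7.8.1 adds: "All adverse events occurring before first intake of trial medication will be assigned to" the screening period. It refers to section 6.1 for the details of the treatment definition.

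**The concern.** One boundary is drawn in two units. The laboratory baseline is separated from later values by clock time, while the table separates screening from treatment by calendar date. A sample taken on Day 1 before the infusion lies between the two. The table puts it on treatment and the baseline rule makes it the reference value. No sentence in the SAP says that the value chosen as baseline is left out of the on-treatment values.

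A programmer who follows the table would let a value obtained before any drug was given compete for the worst on-treatment grade. Patients whose baseline was drawn on an earlier day would be handled differently from those sampled on Day 1, although nothing about their treatment differs. The outputs exposed are the worst on-treatment CTCAE grade, the transitions from baseline to worst and from worst to last value, and the potential Hy's law search, which looks at any on-treatment aminotransferase value and does not require a rise from baseline.

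**Working it through.** The SAP gives no figure on this point to reproduce. The check applies its definitions to a sequence of samples and then counts the grade combinations affected.

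**Step 1: classify each sample.** Baseline eligibility follows section 6.7. On-treatment status is read in two ways: (a) by date, as in Table 6.1:1; (b) by time, as in the text under the table. The grades are invented for illustration.

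| Sample | Grade | Baseline-eligible | On-treatment (a) | On-treatment (b) |
|---|---|---|---|---|
| Screening | 2 | yes | no | no |
| Day 1, pre-dose | 3 | yes | **yes** | **no** |
| Day 1, post-dose | 2 | no | yes | yes |
| Day 8 | 1 | no | yes | yes |
| Day 15 | 2 | no | yes | yes |

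Only the Day 1 pre-dose sample changes status. Baseline is the latest eligible value, grade 3. The worst on-treatment grade is max(3, 2, 1, 2) = 3 under (a) and max(2, 1, 2) = 2 under (b).

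**Step 2: count the combinations affected.** Let b be the grade of a baseline drawn pre-dose on Day 1 and w the worst post-dose grade, each from 0 to 4. That gives 5 × 5 = 25 pairs.

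- Worst on-treatment grade: max(b, w) under (a), w under (b). They differ only if b > w, which happens in 1 + 2 + 3 + 4 = 10 of 25 pairs.
- Improvement from baseline to worst: (a) needs max(b, w) < b, which is impossible, so 0 of 25. (b) needs w < b, so 10 of 25. For Day 1 baselines under (a), the improvement cells of that table are therefore empty by construction.

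**Step 3: possible clinically significant abnormality.** Section 7.8.2 requires grade 2 or higher and a rise of at least one grade over baseline. Under (a) the rise condition is max(b, w) − b ≥ 1, which holds exactly when w − b ≥ 1. In that case max(b, w) = w, so the grade condition is also the same. The two readings differ in 0 of 25 pairs.

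**Step 4: remaining outputs.**

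- Worst to last value: in the same 10 pairs, the transition under (a) starts from a pre-drug value.
- Baseline to last value: affected only if no value was taken after Day 1 pre-dose.
- Potential Hy's law: the combination is ALT or AST above 3 × ULN, total bilirubin at least 2 × ULN and ALKP below 2 × ULN, each event within 14 days of the previous one. Under (a), a pre-dose value can supply part of the combination. This does not depend on b > w, so the count of 10 does not describe it.

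**Step 5: adverse events.** An event starting on Day 1 before the infusion is on-treatment by Table 6.1:1 and screening by the sentence in section 7.8.1. Because that section refers back to 6.1, this is a mismatch of wording.

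**The case against.** The strongest reply is that the SAP already has the right rule. The inequality in section 6.1 concerns adverse event onset and never mentions a laboratory sample. The sentence that speaks of data in general begins at the first administration, and section 4 describes the on-treatment period for events in the same way. A pre-dose sample does not lie between the first administration and the end of the residual effect period. Section 7.8.2 also speaks of post-baseline values, shows baseline separately in the transition tables, and relies on a sponsor laboratory standard that is not at hand and may exclude the baseline record.

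Much of this stands. It means that the double use is one of two readings. A reader might infer that baseline abnormalities will be reported as on-treatment worst grades; the SAP does not establish that, because its own text supports the opposite reading and the actual programming is not visible.

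The reply does not remove the inconsistency. Section 6.1 applies the table to laboratory parameters, and the table excludes a Day 1 record from Screening. The text under the table names no clock time and does not say that it takes precedence. The post-baseline condition selects which patients are displayed; it does not limit the search for the worst value. A sample timed exactly at the first administration is baseline under 6.7 and could still count as on-treatment under either reading.

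On adverse events the reply largely succeeds. Section 7.8.1 defers to 6.1, and the SAP shows clock times only for infusion related reactions, so for other events a date rule may be all that is workable. A reader might also infer that dose limiting toxicity counts or the MTD are affected, since the MTD evaluation period starts on the same date. Nothing in the SAP supports that.

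**Conclusion.** The point holds as an inconsistency to be settled. Table 6.1:1 and the text under it give different answers for a Day 1 pre-dose laboratory sample, and under the table the baseline value can enter the stated safety outputs.

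The effect is limited. For worst-grade outputs it needs three things together: the calendar-date reading, a baseline drawn on Day 1, and later values that are all better than that baseline. For the potential Hy's law search it needs the calendar-date reading and a pre-dose value that contributes to the combination. Where the worst-grade effect occurs it always goes one way: the on-treatment grade is shown as worse than anything observed after dosing. The possible clinically significant abnormality table is untouched.

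The 10 of 25 is a count of possible grade pairs. It says nothing about how many patients are affected, because the SAP does not say how often baseline was drawn on Day 1 or how grades moved afterwards. The laboratory analyses are descriptive, and the SAP ties no decision rule to these tables. The conclusion assumes that the sponsor's laboratory standard does not already exclude the baseline record; if it does, only the SAP wording needs correcting.

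**What to change.** 1. In section 6.1 (with Table 6.1:1) and section 7.8.2, state that on-treatment laboratory values are those taken after the start of the first administration, excluding the value selected as baseline. Use sampling time on Day 1 where it is recorded. Excluding the baseline value also settles a sample timed exactly at the first administration, and an untimed Day 1 sample that section 6.7 assumes to be pre-dose.
2. Say that this definition governs the worst-grade table, the transitions to and from the worst value, and the potential Hy's law search.
3. For adverse events with onset on Day 1, only align the wording of section 7.8.1 with Table 6.1:1. No change to their assignment is needed.

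The cost is a short SAP edit and one condition in the laboratory derivation. No new data are required.
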